An alternative strategy is to apply LTD-like stimulation to the medial prefrontal cortex (LTD-like mPFC rTMS (Strategy 2, Aim 2). This strategy is based on our understanding of functional neural architecture, wherein the SN is modulated by 2 other core networks: the executive control network (ECN) and the default mode network (DMN). As stated above, it is possible to attenuate activity in the SN through LTP-like TMS to the DLPFC, a node in the ECN. It is also possible to attenuate the SN through LTD-like TMS to the ventral medial prefrontal cortex (a node in the DMN). **The proposed study will be the first to employ a randomized, double-blind, sham-controlled design to parametrically evaluate the longitudinal effects of 16 days of rTMS to the DLPFC (Aim 1) or the MPFC (Aim 2) on self-reported pain and the brain's response to pain. This will be done in a cohort of patients recruited from the community as well as MUSC clinics with chronic lower back pain that have not been able to find adequate pain relief, whether or not they are using prescription opiates for 3 or more months.** Participants will be randomized to receive rTMS to the DLPFC (iTBS), MPFC (cTBS), or sham (50% at each site), using a Latin square randomization. Resting state connectivity will be collected 3 times: before the 1st day of TMS, after the 12th day of TMS, and before the 16th day of TMS (the last day administered).

Aim 1. Evaluate DLPFC rTMS as a tool to dampen pain and the engagement of the Pain Network. Hypothesis 1: DLPFC TMS will attenuate the baseline brain response to pain (Pain Network activity) and increase activity in the ECN when the patient is given instructions to ‘control’ the pain.

Aim 2. Evaluate MPFC rTMS as a tool to dampen pain and the engagement of the Pain Network. Hypothesis 1: MPFC TMS will also attenuate the baseline brain response to pain (Pain Network activity) but will not effect the ECN or SN when the patient is given instructions to ‘control’ the pain.

(Exploratory Aim): We will evaluate if there are rate-dependent effects between baseline SN connectivity with the ECN and DMN and the efficacy of each TMS strategy on subjective pain. Data will be analyzed by using multivariate pattern analysis (MVPA) (2014). While the primary outcomes will be MRI V1 vs V2, we will also examine the relative ‘durability’ of the effects on pain by comparing the MRI data at the end of all TMS visits between and within groups with factor analysis.

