Early Feasibility Data: Quantitative Sensory Testing of pain in opiate using individuals after 10 sessions of rTMS (Strategy 1 and 2). Our group recently initiated a 10 day clinical trial of these 2 strategies as tools to decrease behavioral reports of pain. From June 2017 to October 2017 we were able to enroll and successfully acquire Quantitative Sensory Testing data from 10 individuals (5 of whom received each strategy for 10 days). 8 of the 10 remained enrolled for the full treatment. The 2 that didn't finish were terminated due to a Hurricane in our area (Sept 2017). This initial feasibility trial is promising and individuals appear to be receiving pain relief (as demonstrated by their continued engagement). However, without a rigorous sham control group or longitudinal neuroimaging data, the results of this pilot study will be limited to Quantitative Sensory Testing. Through this R21 mechanism we hope to be able to build upon the early success of this trial by including a rigorous, randomized, sham-controlled design which includes neuroimaging data necessary to understand mechanisms of action of these innovative new treatment approaches.

Aims 1 & 2 of this proposal will address the next critical steps in developing DLPFC or MPFC TMS as a new, innovative treatment option for pain: 1) Do multiple sessions of rTMS have a sustainable impact on pain in CLBP patients? And 2) Are there consistent patterns of neural activity to pain that serve as a predictive biomarker for TMS efficacy in these individuals?

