Participants. We will enroll 48 men and women 18-75 years old with CLBP that have a history of current prescription opioid use (>3 months) for the treatment of pain. Participants will be recruited through the community along with MUSC clinics. Patients that have previously agreed to be contacted for research and have current chronic pain will be referred to the study. Our prior history with targeted enrollment (See Significance) indicates this is feasible within 20 months, leading to full completion by 22 months. **Exclusion criteria:** Typical MRI and TMS exclusionary criteria, including metal above the neck or implanted in the body, use of prescription medications that lower seizure threshold, a history of seizures or traumatic brain injury, pregnancy or trying to become pregnant, current substance use or dependence (other than opioids and nicotine), history of seizure disorder, and claustrophobia. Participants will provide written informed consent following explanation of the study. **Sample size estimate:** A power estimate for Aim 1 and 2 was prepared using an original fMRI dataset previously collected in our laboratory (8). In this experiment, 18 healthy controls performed the same fMRI pain paradigm as the present study before and after a single session of 10 Hz rTMS. Mean parameter estimates for the “heat pain vs. rest” condition were extracted from several *a priori* regions of interest. These data yielded an effect size which ranged from 0.70 (thalamus) to 1.08 (insula) (n=15 yields 80% power using a two-sided p<0.05). Allowing for a 10% dropout rate after the screening visit, and up to a 20% dropout rate at the end of the Treatment phase (Week 4), as well as a 10% data loss rate for MRI (Aim 2) due to individuals with excessive head motion in the MRI scanner, screening 58 individuals should lead to complete data from 48 individuals (16 real DLPFC, 16 real MPFC, 16 sham (50% at each site)). Randomization will be handled by the MUSC data coordination center of the Biostatistical Unit ([name], biostatistician) and a Latin Square design with replacement will be used to ensure even enrollment across groups with replacement.

General Methods

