we expect 16 sessions of TMS treatments (3 days per week for 4 weeks, followed by 1 day a week for 4 weeks) will take 8 weeks, allotting time for a weekend (as is conventional in this field), holidays and/or one missed appointment. In the event that an individual drops out before completing the 16 TMS sessions, the number of sessions received will be a covariate in the analyses. Cortical Targeting: After the MRI scans participants will be escorted into the Brain Stimulation room (30 feet away) where scalp localization will be performed for the TMS procedure. The Cartesian position of the coil (X,Y,Z) will be determined by standardized positions from the EEG 10-20 system: 1) F3 (left DLPFC stimulation (Aim 1)), 2) FP1 (MPFC stimulation (Aim 2)). The angular position of the coil (pitch, yaw, roll) will be determined by the individual's cortical geography beneath FP1 and F3 using the individual's T1 scan for guidance. The locations and coil orientation will be indicated on a nylon cap which will be worn during the TMS sessions. We will then determine the participant's resting motor threshold (RMT, the minimal amount of stimulation required over the hand area of the primary motor cortex to induce contraction of the APB muscle of the hand 50% of the time) via the standardized PEST procedure (106, 107). During each TMS session, we will take a non-identifiable photo of the participants' forehead (eyes covered with an index card) to ensure the coil is correctly placed each time they return to the lab. This will be cross-checked with the neuronavigation data.

Strategy 1: iTBS to the left dlPFC. For intermittent theta burst stimulation (Aim 1), participants will receive 20 trains of stimulation over the dlPFC (middle frontal gyrus) (F3) (each train: 3 pulse bursts presented at 5Hz, 15 pulses/sec for 2 sec, 8 sec rest, 200 pulses/train; 110% RMT, MagPro; 600 pulses total) using a figure 8 coil (Coil Cool-B65 A/P).

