Strategy 2: cTBS to the vmPFC. For continuous theta burst stimulation (Aim 2), participants will receive 1 train of stimulation over the left frontal pole (FP1) (each train: 3 pulse bursts presented at 5Hz, 15 pulses/sec for 40 sec, 600 pulses/train, 110% RMT, MagPro; 600 pulses total) using a figure 8 coil (Coil Cool-B65 A/P). This protocol has been shown to attenuate the mPFC and striatum in cocaine dependent individuals in the past (61-63) and has been more effective than 1200 or 1800 pulses of cTBS in attenuating depression (The time between the end of the TBS procedures and the beginning of the behavioral assessments, as well as the scalp-to-cortex distance (which effects the actual TMS dose given to the cortex) will be compiled and used as covariates in subsequent analyses.

ACTIVE SHAM system. The MagVenture MagPro system has an integrated, active sham which passes current through two surface electrodes placed on the scalp. The electrodes will be placed on the left frontalis muscle for all sessions. A patient ID card will randomize participants to receive either real or sham stimulation. This system maintains blinding by a gyroscope in the coil which indicates to the clinical staff whether the coil should be rotated up or down for this participant once the card is entered into the machine. One side of the coil is active, the other is sham. The integrity of the double-blind procedure will be assessed by asking the patients and study personnel rate their confidence regarding whether they thought they received real or sham (scale 1-10).

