A. Quantitative Sensory Testing. The QST pain assessment produces 3 output variables: sensory threshold, pain threshold, tolerance threshold (all expressed in degrees Celsius). The hypothesis will be tested using a within-subject repeated measures design (time x treatment) wherein time is the repeated variable and Real or Sham TMS is the grouping variable. Given that the purpose of this pilot study is to develop effect sizes for a subsequent R01, we will derive least-squares means effect sizes of this strategy on these thresholds. Secondary analyses will evaluate the relationship between QST levels and the neural response to pain, as well as the relationship between QST values and evoked cortical responses. Integrating these measures together will provide a more complete picture of how cortical activity is able to modulate the pain response.

B. Questionnaires and Evaluations. The Opiate Pain inventory produces 4 output variables of interest: level of discomfort, level of pain, urge to use opiates, amount willing to pay for an opiate. The hypotheses for the Aims will be tested using a within-subject repeated measures design (time x treatment) wherein time is the repeated variable and Real or Sham TMS is the grouping variable. Given that the purpose of this pilot study is to develop effect sizes for a subsequent R01, we will derive least-squares means effect sizes of our research strategy on these 4 variables, to determine the unique contributions of this intervention.

C. Neuroimaging Data (Aim 2): Immediately following acquisition, functional structural data will be uploaded to a secure data server and converted to NIfTI format. All preprocessing and analyses will be

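### The only analysis rule for dropouts is to covary for sessions received, a post-randomisation variable; the adjusted arm effect need not be the effect of assignment, and missing outcomes are left unhandled

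*Combined protocol and SAP*

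**What the plan says.** Randomisation follows the screening visit and precedes all stimulation. Sixteen sessions are planned: three a week for four weeks, then one a week for four weeks. For anyone who stops early, section 10.0 (rTMS treatment sessions) says that "the number of sessions received will be a covariate in the analyses".

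The sample size paragraph allows for "up to a 20% dropout rate at the end of the Treatment phase (Week 4"), and says that "a Latin Square design with replacement will be used to ensure even enrollment across groups with replacement". The replacement provision concerns enrolment. It does not say how the data of those who leave are analysed.

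The Data Analysis Plan (parts A and B) specifies a "within-subject repeated measures design (time x treatment) wherein time is the repeated variable and Real or Sham TMS is the grouping variable", summarised by least-squares means effect sizes for a later R01. It names no estimation method, analysis set or missing-data assumption, and does not say how sessions received would enter.

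On outcomes, section 1.0 says "While the primary outcomes will be MRI V1 vs V2", whereas the Assessments paragraph of section 10.0 takes the primary measures from quantitative sensory testing (QST).

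The Strategy 2 paragraph adds another covariate: "The time between the end of the TBS procedures and the beginning of the behavioral assessments", together with scalp-to-cortex distance, "will be compiled and used as covariates in subsequent analyses".

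**The concern.** The number of sessions a person receives is known only after assignment. It can respond to the treatment (relief, discomfort, disappointment with sham) and to how the person would have fared anyway. The plan makes the first link itself: in the feasibility data, "individuals appear to be receiving pain relief (as demonstrated by their continued engagement"). Conditioning on such a variable can open a difference between arms that randomisation had removed, or take out part of the effect being estimated.

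Two further matters follow. The covariate does not supply outcomes that were never measured, so the missing-data question stays open at a dropout rate the plan itself foresees. And if the full-course count is used for MRI V1 versus V2, some of the counted sessions come after that outcome and may depend on it.

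The pilot's stated product is a set of effect sizes for the next trial, so what those effect sizes estimate matters beyond any p-value.

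**Working it through.** **1. How many people the rule touches.** Inputs from the sample size paragraph: 48 enrolled, 58 screened, 10% lost after screening, up to 20% lost by Week 4, 10% MRI data loss.
- On 48 enrolled: 48 × 0.20 = 9.6.
- On 58 screened: 58 × 0.90 = 52.2 remain; 52.2 × 0.20 = 10.4.

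So about 10 people at the plan's upper rate. The plan's own yield of 48 complete from 58 does not reproduce when all three losses are applied (58 × 0.9 × 0.8 × 0.9 = 37.6). That is a separate matter and is not used here.

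**2. Sessions after MRI V2.** Section 10.0 places V2 after 12 days of rTMS (MRI Visits 1-3) or before the 12th visit, hence after 11 sessions (Overview). Of 16 sessions, 16 − 12 = 4 (25%) or 16 − 11 = 5 (31%) come after V2.

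**3. Precision for scale.** Assume unit variance and a correlation of 0.7² = 0.49 between visits. The SD of the baseline-to-V2 change is √(2 × 0.51) = 1.01.
- One active arm against sham, 16 v 16: 1.01 × √(2/16) = 0.357.
- Both active arms against sham, 32 v 16: 1.01 × √(1/16 + 1/32) = 0.309.

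**4. Effect of the covariate in the planned model.** The documents give no inputs for this, so every parameter below is assumed.
- Setup: outcomes at baseline, week 2 and V2, unit variance, correlation 0.49; real to sham 2:1; true effect 0 or 0.5 SD at V2 and half that at week 2.
- Dropout between week 2 and V2 is logistic in the week 2 outcome (slope 0, 1 or 2) and arm (coefficient −1, 0 or +1), set to 20% overall. This gives 2 × 3 × 3 = 18 scenarios of 600,000 people each.
- Sessions are 6 to 11 for dropouts and 16 otherwise.

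Results for the baseline-to-V2 time by treatment contrast:
- *Complete data.* A sessions main effect shifts it by 0.000 SD, because a term constant over time cancels from a within-person change. A sessions by time term shifts it by 0.0007 or less.
- *V2 missing after dropout; likelihood model, all visits.* Without sessions, bias is within 0.005 SD in all 18 scenarios. This is expected, because dropout depends only on arm and an observed outcome. Adding sessions shifts the contrast by 0.0012 SD or less in 8 scenarios and by −0.055 to +0.033 SD in the other 10.

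The 8 are the six with dropout unrelated to outcome, plus the two with no treatment effect and no arm coefficient, where dropout does not differ by arm. In the other 10, dropout depends on outcome and differs by arm. The largest shift is 0.055/0.357 = 0.15 to 0.055/0.309 = 0.18 of a standard error.

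**5. Another model form.** In a baseline-adjusted comparison at V2 with outcomes observed after dropout, the same 18 scenarios give shifts of −0.031 to +0.054 SD.

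**6. TBS-to-assessment delay.** It arises at each session, after randomisation. It has no value at the baseline assessment, before any TBS, nor for the pain ratings taken before a session (SubAim 1). It therefore cannot enter a model of all visits as written. Scalp-to-cortex distance taken from the first scan is a baseline measure and is not open to this objection.

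**The case against.** The strongest reply is that the harm is small in the model the plan names: nil with complete data, and under 0.2 of a standard error in the assumed incomplete-data scenarios. A trial of this size could not detect that. This stands, and it limits the weight of the point.

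It can also be said that the documents never declare the effect of assignment as the target, and that a dose-adjusted effect is a coherent pilot quantity. That is fair as far as it goes. But the design is randomised and sham-controlled, and the effect sizes are to be taken relative to sham. A dose-adjusted effect can be reported beside the randomised comparison; the plan offers nothing in its place for dropouts.

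Several stronger readings are tempting and are not supported:
- *That the bias is large.* Bigger figures can be produced. A baseline-adjusted V2 comparison with sessions counted to 16 and a further 10% later dropout driven by V2 outcome and arm gives up to +0.120 SD. A final-value comparison with benefit proportional to sessions and dropout of 33% v 13% gives 0.69 adjusted against 0.55 by assignment; with equal dropout the two agree at 0.60. The plan states neither those models nor those dropout patterns.
- *That the feasibility data show dropout driven by pain relief.* Section 2.0 reports that the two non-finishers were terminated because of a hurricane.
- *That the count certainly runs to 16 for MRI V1 versus V2.* The rule does not say so; it could mean sessions up to that assessment. MRI is also not the undisputed primary outcome, since the Assessments paragraph names QST.
- *That the delay biases the arm comparison.* Nothing shows that it differs by arm, and its place in the Strategy 2 paragraph leaves its scope unclear.

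**Conclusion.** The point holds in limited form. The plan firmly commits to adjusting for a post-randomisation variable as its sole analysis rule for dropouts. The adjusted arm effect need not be the effect of assignment, and missing outcomes have no stated handling. If the full-course count is applied to MRI V1 versus V2, 4 or 5 of the 16 sessions come after the outcome.

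The size of any bias cannot be known from the documents. The figure of about 0.055 SD at most, in the planned time by treatment model, rests wholly on the assumed correlation, effect, dropout mechanism and 20% rate. The missing-data gap does not depend on that figure. The change is worth making before analysis; it is not a reason to doubt the design. The delay is a secondary point, with no bias shown. The opioid covariates, and the conflict over whether all participants use opioids, are separate matters.

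**What to change.** Replace the rule for dropouts in section 10.0, and add to Data Analysis Plan A and B:
- Keep sessions received out of the main arm by time models.
- Estimate arm effects in all randomised participants, by assigned arm, using every available visit, in a likelihood-based mixed model that includes the baseline outcome. State that it assumes outcomes are missing at random given the observed data.
- Report sessions received by arm.
- Label any sessions-adjusted analysis exploratory, and count only sessions before the outcome being analysed.
- Treat TBS-to-assessment delay the same way. Scalp-to-cortex distance may stay.

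The cost is wording; no new data are needed. The downside is that dose-adjusted results become exploratory, and the main estimate relies on missing at random, which the data cannot confirm.

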The Brain Stimulation Laboratory (BSL) is located in a series of labs and offices (>3000 square feet) primarily located on the 5th floor of the Institute of Psychiatry (IOP). BSL studies use electromagnetic approaches as either research tools investigating neuroscience questions or as investigational or FDA approved treatments for brain diseases. Techniques actively being used by BSL researchers and their collaborators include: transcranial magnetic stimulation (TMS), vagus nerve stimulation (VNS), transcranial direct current stimulation (tDCS), electroconvulsive therapy (ECT), deep brain stimulation (DBS) and epidural cortical stimulation (epCS). MUSC's BSL team has been a world leader in TMS research since 1995, performing basic research studies using TMS as well as using TMS in clinical trials for depression, pain and addiction.

Facilities and Resources Specific to the PI:

[name] primary office and laboratory is in the Brain Stimulation Division of the Department of Psychiatry. She will utilize the resources of the Brain Stimulation Laboratory.

[name] manages the BSL suite located in the Center for Biomedical Imaging along with [name]. This suite contains a room (10ft x 10 ft.) dedicated for TMS stimulation. This room currently contains 2 computers, a desk for patient interviewing, and a Magstim Bistim TMS system.

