Statistical review of the study, will be conducted by a faculty member from the MUSC Provost-sponsored Biostatistical Collaborative Unit (see Facilities) (including enrollment, retention, assessment inventories) annually. Data collected in previous studies by our research group have demonstrated that after extended use in the MRI scanner environment (likely more than 5000 pulses) the strength of the induced magnetic field from the Magstim biphasic coil begins to drop in a non-linear fashion. Consequently, the intensity of the induced magnetic field from the Magstim coil will be assessed by study personnel and logged weekly (alongside with use records from that week, number of pulses, intensity of pulses). This cumulative record of coil performance will be monitored and, when the intensity of the induced field had degraded 10%, we will switch to a new, identical Magstim coil. We do not anticipate this will occur within the 2-year period of this project.

Confidentiality and Privacy:

Section 301(d) of the Public Health Service Act, November 4, 1988 provides a layer of protection for health data reported by participants that have volunteered for federally funded research studies. Only members of the research team will have access to participant records. Records will be kept in a locked file cabinet in a locked office. Computer records are password protected and will identify participants by Patient ID number.

Definition and Reporting of AEs/SAEs to the IRB/FDA/NIDA:

An AE is defined as any untoward medical occurrence in a study subject administered rTMS that does not necessarily have a causal relationship with this treatment. Any unwanted change, physically, psychologically or behaviorally, that occurs in a study participant during the course of the trial is an adverse event. A Serious Adverse Event (SAE) is defined as an adverse event that has one of the following outcomes: death, life-threatening, inpatient hospitalization or prolongation of existing hospitalization, persistent or significant disability/incapacity, a congenital anomaly/birth defect.

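### The Strategy 1 iTBS dose line prints 200 pulses per train where its other entries give 30; the coil-output clause and the IRB precedent wording also need small corrections

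*Combined protocol and SAP*

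**What the plan says.** **Dose line (Section 10.0, Strategy 1).** Participants receive 20 trains over F3. Each train consists of 3-pulse bursts at 5 Hz, with the remaining settings printed as "15 pulses/sec for 2 sec, 8 sec rest, 200 pulses/train; 110% RMT, MagPro; 600 pulses total". The coil is a MagPro Cool-B65 A/P. No other part of the document gives the stimulation parameters for this strategy. The companion line for Strategy 2, continuous theta burst in a single train at FP1, reads "15 pulses/sec for 40 sec, 600 pulses/train, 110% RMT, MagPro; 600 pulses total", on the same coil.

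**Coil-output clause (Section 13.0, Quality assurance plan).** The plan states that "the intensity of the induced magnetic field from the Magstim coil will be assessed by study personnel and logged weekly". A usage log is kept with that check, and a replacement rule follows: once output has fallen by 10%, "we will switch to a new, identical Magstim coil". The reason given is that a Magstim coil loses field strength after prolonged use in the scanner. The team does not expect that to happen during the project. Section 13.0 also states, under conflict of interest, that the study device is made by MagVenture.

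**IRB precedent (Sections 15.0 and 18.0).** Each section reports that continuous theta burst stimulation at the DLPFC and one other site, described as identical to what is done in this protocol, was designated minimal risk. Sections 1.0 and 10.0 assign intermittent stimulation to the DLPFC and continuous stimulation to the medial prefrontal site.

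**The concern.** A dose line should give the operator and any later reader one answer. This one gives two, because its pulses-per-train entry conflicts with its own rate, on-time, train count and total. It is the only definition of the treatment in one of two active arms, and the pilot's stated purpose is to supply effect sizes for a subsequent R01, so the next protocol is likely to copy the parameters from here.

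The coil clause has a different fault. Followed literally, staff would test and log a coil that the document gives no part in treatment, and nothing written would cover the coil that is used. The precedent wording offers, as risk support for the DLPFC arm, a stimulation pattern that the arm does not use. Section 2.0 itself treats the two patterns as opposite in effect: intermittent as LTP-like, continuous as LTD-like.

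**Working it through.** **Inputs, all from Section 10.0.** Strategy 1: 3 pulses per burst, 5 bursts per second, 2 s on, 8 s rest, 20 trains, 200 pulses per train (printed), 600 pulses total (printed). Strategy 2: 15 pulses per second, 40 s, 1 train, 600 pulses per train, 600 total.

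**Reproducing the printed total for Strategy 1**
- Rate: 3 x 5 = 15 pulses/s, as printed.
- Pulses per train = rate x on-time = 15 x 2 = 30, which is 10 bursts of 3.
- Session total = 30 x 20 = 600, as printed.
- Back-check: 600 / 20 = 30.

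**Trying the printed 200 pulses per train**
- With 20 trains: 200 x 20 = 4,000 pulses, or 4,000 / 600 = 6.67 times the printed total.
- With the total held at 600: 600 / 200 = 3 trains, not 20.
- With 2 s on: 200 / 2 = 100 pulses/s, not 15.
- At 15 pulses/s: 200 / 15 = 13.3 s per train, not 2 s.
- In 3-pulse bursts: 200 / 3 = 66.7, not a whole number.

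No reading keeps the 200 without changing at least one other entry. Replacing it by 30 leaves every other entry as printed.

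**Control: Strategy 2.** 15 x 40 = 600 per train, and 600 x 1 = 600 total. That line is consistent, so the 200 does not reflect some other way of counting pulses per train.

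**A possible source.** 20 x (2 + 8) = 200 s is the session length counting each train with its rest, so the 200 may be a duration in the wrong slot. This is a guess, and nothing below depends on it.

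**Participants under the line.** The sample size paragraph plans 16 real DLPFC, 16 real MPFC and 16 sham, with half of the sham group at each site. That is 16 on real DLPFC stimulation. If sham at that site follows the same settings, which the document does not say outright, add 16 x 0.5 = 8, giving 24 of 48.

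**Device wording, side by side**

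| Place | Device named |
|---|---|
| 10.0, Strategies 1 and 2 | MagPro, Coil Cool-B65 A/P |
| 10.0, active sham | MagVenture MagPro |
| 13.0, conflict of interest | MagVenture |
| 13.0, weekly output check, log and replacement | Magstim coil |

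**Precedent wording, side by side**

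| Place | Pattern at the DLPFC | Other site named |
|---|---|---|
| 10.0, Strategy 1 (this trial) | Intermittent | n/a |
| 15.0, reported precedent | Continuous | Motor cortex |
| 18.0, reported precedent | Continuous | Medial prefrontal |

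The Section 18.0 statement fits the medial prefrontal arm. Neither statement describes the DLPFC arm.

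**The case against.** The strongest reply is that these are clerical slips and that the main one corrects itself: four entries in the same parenthesis agree on 30, the 600 total is explicit, and it matches Strategy 2. That stands as to consequence, and it limits the weight of the point. It does not make the printed number right.

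On the coil, the clause rests on Magstim output loss in the scanner, whereas treatment here is given in a separate room 30 feet away. It may be carried-over text, and deleting it would remove the mismatch as well as redirecting it would. That stands too, so either remedy is acceptable.

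A reader might infer more than the documents support:

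- *That participants would receive a wrong dose or that effect sizes would be biased.* The intended dose can be worked out from the line itself, and nothing shows that 4,000 pulses would be given.
- *That the dose covariates are undermined.* The plan says "the number of sessions received will be a covariate in the analyses", but only for participants who drop out before completing all 16 sessions, and pulses per session are fixed at 600 in both strategies. Scalp-to-cortex distance, included as something "which effects the actual TMS dose given to the cortex", depends on neither the misprint nor the coil name.
- *That the treatment coil loses output unnoticed.* The documents give no loss rate for the MagPro coil, so counting the pulses it would deliver measures no harm.
- *That the wrong machine is in use.* Section 7.0 says "This room currently contains 2 computers, a desk for patient interviewing, and a Magstim Bistim TMS system", but that is a facilities description, and Section 10.0 names the treatment device plainly.
- *That the two IRB statements contradict each other.* They differ on the second site and on the population (opiate dependence in 15.0, nicotine dependence in 18.0), but they may report separate designations, both true. Forcing them to agree could make an accurate report false. The FDA sentence beside each is not in question.

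**Conclusion.** The point holds as a correction to operative text. One entry in the Strategy 1 dose line is wrong: 200 is printed where 30 is implied. It affects the definition of treatment for the 16 real-DLPFC participants and plausibly about 8 sham participants at that site; the 8 assumes that sham follows the same line. Taking 30 as the intended value rests on the agreement of rate, on-time, train count and total. Sample size, power and the analysis are untouched.

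Second in weight, the output check, pulse log and 10% replacement rule are written for a coil with no stated treatment role. Third, and a matter of wording only, the claim that the earlier stimulation was identical to this protocol's is not correct for the DLPFC arm.

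**What to change.** 1. **Section 10.0, Strategy 1.** Replace the 200 with *30 pulses/train (10 bursts of 3)*. Keep 20 trains and 600 pulses total. Cost: one number.
2. **Section 13.0, Quality assurance plan.** Either apply the weekly check, the pulse log and the 10% replacement rule to the MagPro Cool-B65 A/P coil, with replacement by the same model, or delete the clause if its in-scanner rationale does not apply. The first option costs a short weekly check on a coil that the documents do not show to degrade. The second costs nothing but leaves no written output check.
3. **Sections 15.0 and 18.0.** Qualify the statement that the earlier stimulation was identical to this protocol's, noting that the DLPFC arm here is intermittent. Leave the reported sites and populations as they are unless the sponsor's records show an error. Cost: a few words in each section.

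None of these changes alters visits, endpoints, sample size or analysis.
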